3 SYNOPSIS

Name of Sponsor/Company: Hill Dermaceuticals, Inc.
Name of Finished Product: Clobetasol Topical Oil
Name of Active Ingredient: 0.05% clobetasol propionate
Study Title: Open-Label Study of the Pharmacokinetics and Safety Including HPA Axis Suppression Potential of Clobetasol Topical Oil in Pediatric Subjects with Moderate to Severe Atopic Dermatitis
Study Number: CP 0418 SS-P2 051
Study Center(s): Up to 12 study centers in the United States (US)
Number of Subjects Planned: Up to approximately 72 subjects will be enrolled to achieve ≥ 20 completed subjects per cohort.
Study Period: The study duration for each subject will be up to 54 days (up to 38 days for Screening assessments, followed by up to 16 days of treatment and follow-up). Additional time will be required for subjects requiring additional hypothalamic-pituitary-adrenal [HPA] axis function testing due to an abnormal result at End of Treatment.
Phase of Development: 1/2
Rationale: This study is designed to evaluate the safety and HPA axis suppression potential of Clobetasol Topical Oil and systemic exposure to clobetasol when Clobetasol Topical Oil is applied to pediatric subjects with moderate to severe atopic dermatitis (AD) under maximal use conditions.
Objectives: The objectives of this study are to assess the following properties of Clobetasol Topical Oil under maximal use conditions in pediatric subjects with moderate to severe AD: 
 • Safety, including the potential to suppress the HPA axis • Systemic exposure to clobetasol following repeated application
Design and Methodology: This study is a multicenter, open-label study designed to evaluate the HPA axis suppression potential and systemic exposure to clobetasol, when administered as Clobetasol Topical Oil in pediatric subjects, under conditions consistent with anticipated clinical use and under conditions designed to maximize the potential for drug absorption in subjects with moderate to severe AD. The study will consist of three successively younger pediatric cohorts, as safety data allow: 
 • Cohort 1: ≥ 12 to < 18 years; • Cohort 2: ≥ 6 to < 12 years; and • Cohort 3: ≥ 2 to < 6 years. Enrollment into each successively younger pediatric cohort will proceed only after the preceding cohort has been completed and safety and exploratory data (including adverse events [AEs], tolerability assessments, clinical laboratory results, and the percentage of subjects with HPA axis suppression) have been reviewed and agreed to be acceptable for progression to the next cohort. Enrollment into Cohorts 2 and 3 will proceed only if the percentage of subjects with HPA axis suppression in Cohorts 1 and 2, respectively, is $\leq 40\%$.

Name of Sponsor/Company: Hill Dermaceuticals, Inc.
Name of Finished Product: Clobetasol Topical Oil
Name of Active Ingredient: 0.05% clobetasol propionate

HPA axis suppression is defined as a cortisol concentration $\leq 18 \mu\text{g}/100 \text{ mL}$ at approximately 30 minutes after stimulation with cosyntropin.
 
Starting with Cohort 1 (and continuing with each successively younger pediatric cohort as safety data allow), the study will start with the Screening visit, at which potentially eligible subjects will provide assent and at least one parent and/or guardian will provide informed consent, as applicable. Subjects will then undergo screening evaluations to include an abbreviated physical examination, assessments of their AD (to include an Investigator Static Global Assessment [ISGA] and the percent of total body surface area [BSA] affected by AD as assessed by the investigator), and an evaluation of medical history. Urine will be obtained for pregnancy screening for female subjects of childbearing potential. Prior and concomitant medications will be reported, AEs will be assessed, and blood samples will be taken for clinical laboratory tests (chemistry and hematology). An HPA axis suppression test (cosyntropin stimulation test) will be performed. The Screening visit will start 14 to 38 days (i.e., Day -13 to Day -37) before the start of study drug, to allow for washout of prior medications and due to the requirement that the HPA axis suppression test at Screening be performed ≥ 28 days before the second HPA axis suppression test which will be performed at the Day 15 (End of Treatment) visit.
 
Subjects with moderate to severe AD and who meet all other eligibility criteria will be scheduled to return to the clinic for the Baseline/Start of Treatment visit on Day 1.
 
At the Baseline/Start of Treatment visit, subjects will undergo assessments of their AD, baseline (pretreatment) assessments of tolerability criteria, a review of eligibility criteria, a urine pregnancy test (for female subjects of childbearing potential) and baseline (pretreatment) assessments of AEs. For subjects who remain eligible for the study, the investigator will designate the areas to be treated with study drug, and subjects and/or their caregivers will apply the first dose of study drug at the site. AEs and tolerability will be assessed.
 
Subjects and/or their caregivers will continue to apply study drug to the affected areas twice daily (morning and evening), at approximately the same times each morning and each evening, up until their next visit. Subjects and/or their caregivers will treat the designated areas for the duration of the dosing period even if the areas begin to improve.
 
Subjects will return to the clinic for a Week 1 visit on Day 8 (with a window of ± 1 day). Evaluations performed at the Week 1 visit will include assessments of AD, tolerability, and AEs. Subjects will return all study drug from the previous week, and a new supply of study drug will be dispensed for the upcoming week.
 
Subjects and/or their caregivers will be instructed to continue applying study drug up through the evening immediately preceding their scheduled End of Treatment visit.
 
Subjects will return to the clinic for the End of Treatment visit on Day 15 with a window of +1 day (i.e., as late as Day 16). In advance of this visit, subjects will be instructed to bring their study drug to the site and not to apply any study drug doses on the day of this visit until told to do so at the site; these instructions will be provided so that dosing can be coordinated with the pharmacokinetic (PK) blood sampling that will occur during this visit. At this visit, PK blood samples will be taken predose (this sample will be taken within 12 ± 2 hours of the previous evening's application of study drug and within 1 hour before the application of study drug on the day of this visit) and at the following times following the application of study drug on the day of the visit: 1 h (± 10 minutes), 3 h (± 15 minutes), and 6 h (± 1 hour). Other procedures performed at the End of Treatment visit will include an HPA axis suppression test (which must


Name of Sponsor/Company: Hill Dermaceuticals, Inc.
Name of Finished Product: Clobetasol Topical Oil
Name of Active Ingredient: 0.05% clobetasol propionate

be at least 28 days after the Screening HPA axis suppression test), and assessments of AD, tolerability, and AEs. A urine pregnancy test will be performed for female subjects of childbearing potential. Blood samples will be taken for clinical laboratory (chemistry and hematology) tests.
 
Any subject with a poststimulation cortisol concentration $\leq 18 \mu\text{g}/100 \text{ mL}$ at the End of Treatment visit will be re-tested 4 weeks later and followed clinically until recovery of HPA axis function has been demonstrated or until the lack of recovery can reasonably be explained.
 
If all three cohorts are completed, approximately 72 subjects will be enrolled.

Study Visits:
 
Screening (Day -37 to Day 0); Baseline/Start of Treatment (Day 1); Week 1 (Day 8\pm1 day); End of Treatment (Day 15+1 day)

Pharmacokinetic Evaluations for Clobetasol:
 
 • Maximum observed plasma concentration (C_{max}) • Time of maximum observed plasma concentration (T_{max}) • Area under the curve from time 0 to 6 hours ($\text{AUC}_{(0-6)}$)

Safety Evaluations:
 
 • HPA axis suppression test • AEs • Clinical laboratory evaluations • Urine pregnancy tests for females of childbearing potential

Exploratory Evaluations:
 
 • Percent of total BSA involvement with AD • ISGA • Tolerability assessments

Key Inclusion Criteria:
 
 • Male or female subjects in good general health confirmed by medical history. • Subjects with a clinical diagnosis of AD (according to the criteria of Hanifin and Rajka) of moderate to severe intensity (ISGA score of 3 or 4) involving $\geq 25\%$ to $\leq 50\%$ of total BSA located within treatable areas (Cohort 1), or $\geq 35\%$ to $\leq 50\%$ of total BSA located within treatable areas (Cohorts 2 and 3), with treatable areas including all but the face, axillae, groin, and scalp. • Subjects with a normally functioning HPA axis, defined as a prestimulation serum cortisol level $> 5 \mu\text{g}/100 \text{ mL}$, and a response to cosyntropin stimulation to $> 18 \mu\text{g}/100 \text{ mL}$ (after approximately 30 minutes); both blood draws for this test should be performed in the morning, if possible. • Female subjects of childbearing potential must have a negative urine pregnancy test, must not be breastfeeding, and must agree to use an acceptable form of birth control for the duration of the study. Female subjects of childbearing potential are defined as all female subjects who have reached menarche and are not two years postmenopausal or who have reached menarche and have not had a hysterectomy, bilateral tubal ligation, and/or complete bilateral oophorectomy.

Name of Sponsor/Company: Hill Dermaceuticals, Inc.
Name of Finished Product: Clobetasol Topical Oil
Name of Active Ingredient: 0.05% clobetasol propionate
Key Exclusion Criteria: 
• Subjects who do not have a normally functioning HPA axis (as defined in the inclusion criteria).• Subjects with an abnormal sleep schedule or who work at night.• Subjects who have used topical dermal corticosteroids or topical immunomodulators (e.g., tacrolimus or pimecrolimus) within 3 weeks before Day 1, and subjects who are using any systemic medication known to affect cortisol levels or HPA axis integrity, systemic corticosteroids, an acute systemic course of corticosteroids, and/or any biological medication within 30 days before Day 1.• Subjects with concomitant medical or dermatologic disorders (neurodermatitis, skin atrophy, striae, telangiectasia, etc.) that may interfere with study objectives and/or evaluations.• Subjects with active skin infection.• Subjects with any known significant endocrinological disorder that may require prohibited treatment, any known underlying disease that the investigator deems uncontrolled and poses a safety risk for the subject while participating in the study, known sensitivity to any ingredient of the study preparation, or a history of adverse responses to topical or systemic steroid therapy.• Subjects who are pregnant or nursing.• Subjects who have used bleach baths, phototherapy, and/or tanning beds, and/or who have had excessive sun exposure within 1 week before Day 1 and/or are planning to use any of these during the study.• Subjects who have participated in a clinical drug or device research study and/or used any investigational treatment within the last 30 days before Day 1.
Test Product, Dose, and Mode of Administration: 
Clobetasol Topical Oil Active ingredient: 0.05% clobetasol propionate Other ingredients: refined peanut oil, mineral oil, oleth-2, and isopropyl myristate Mode of administration: Subjects (and/or their caregivers, as appropriate) will be instructed as following: Blot dry the skin areas to be treated, using a towel, then moisten the skin areas to be treated, using the supplied spritzer according to the supplied instructions. Finally, apply study drug as a thin film to the areas identified by the investigator or designee. Apply study drug twice daily (morning and evening).

Name of Sponsor/Company: Hill Dermaceuticals, Inc.
Name of Finished Product: Clobetasol Topical Oil
Name of Active Ingredient: 0.05% clobetasol propionate
Statistical Analyses: 
The safety parameter of HPA axis suppression will be summarized at the completion of each study cohort and at the end of the study. The percentage of subjects (within cohort) who at the End of Treatment visit demonstrated a poststimulation cortisol concentration $\leq 18 \mu\text{g}/100 \text{ mL}$ will be determined and will inform subsequent cohort enrollment.
 
At the end of the study, cortisol concentrations (both before and after stimulation with cosyntropin) and the percentage of subjects with HPA axis suppression will be summarized both by cohort and across all subjects.
 
Clobetasol plasma concentrations will be summarized across subjects for each sampling time in aggregate and by cohort. PK parameters (C_{max}, T_{max}, and $\text{AUC}(0-6)$) will be calculated using non-compartmental analyses.
 
ISGA results will be summarized at each time point by the number and percentage of subjects in each ISGA category. A combined category for an ISGA score of either 0 or 1 (clear or almost clear) will also be included. In addition, the number and percentage of subjects with an improvement in ISGA score of at least 2 grades from Baseline to each post-Baseline evaluation will be determined, as will the number and percentage of subjects with an ISGA score of either 0 or 1 (clear or almost clear) and an improvement of at least 2 grades from Baseline to each post-Baseline evaluation.
 
Descriptive statistics for continuous measures will include the number of subjects (N), arithmetic and geometric mean, standard deviation (SD), median, minimum, maximum, and confidence interval (CI), where appropriate. Categorical and binary variables will be summarized by the frequency count (n) and percentage (%) of subjects with non-missing data per category.
 
No imputation will be made for missing data.
 
All AEs occurring during the study will be recorded and classified using terminology from the Medical Dictionary for Regulatory Activities (MedDRA). All AEs which start after the start of study drug or which increase from Baseline in severity will be considered treatment emergent adverse events (TEAEs). TEAEs will be summarized by number of events and number and percentage of subjects experiencing TEAEs, across all subjects and by cohort.
 
When summarizing TEAEs by severity or relationship to study drug, each subject will be counted only once within a system organ class or a preferred term using the event with the greatest severity or causality, respectively, within each category.
 
All reported serious AEs (SAEs) will be summarized by the number of subjects reporting the event, system organ class, preferred term, severity, and relationship to study drug.

Sample Size: 
The sample size for this study (approximately 24 subjects in each of Cohorts 1, 2, and 3) is in order to achieve ≥ 20 evaluable subjects within each cohort. Additional subjects may be enrolled if necessary to achieve ≥ 20 evaluable subjects within each cohort.

4	TABLE OF CONTENTS	
1	PROTOCOL APPROVAL	2
2	STUDY ACKNOWLEDGEMENT	3
3	SYNOPSIS	4
4	TABLE OF CONTENTS	9
4.1	List of Tables	11
4.2	List of Abbreviations	12
5	INTRODUCTION	13
5.1	Atopic Dermatitis	13
5.2	Clobetasol Topical Oil	13
5.3	Study Rationale	14
5.4	Rationale for Study Design	14
6	STUDY OBJECTIVES	15
7	STUDY DESIGN	16
7.1	Number of Subjects	17
7.2	Investigators	17
7.3	Study Duration	18
8	STUDY SUBJECTS	19
8.1	Inclusion Criteria	19
8.2	Exclusion Criteria	20
8.3	Subject Completion	20
8.4	Subject Discontinuation	21
8.5	Subjects Lost to Follow-Up	21
9	CONCOMITANT THERAPIES	22
9.1	Permitted Medications	22
9.2	Prohibited Medications	22
10	STUDY SCHEDULE	24
10.1	Schedule of Assessments	24
10.1.1	Screening (Day -37 to Day 0)	25
10.1.2	Baseline/Start of Treatment (Day 1)	26
10.2	One Week (Day 8)	27
10.3	End of Treatment (Day 15)	28
10.4	Unscheduled	28
10.5	Post-study Follow-up	29
10.6	Missed Visits	29
10.7	Subject Completion	29
10.8	Early Study Termination	29
11	STUDY PROCEDURES	30
11.1	Medical/Medication History	30
11.2	Abbreviated Physical Examination	30
11.3	Urine Pregnancy Test	30
11.4	HPA Axis Suppression Test	30
11.5	Assessments of AD	31
11.5.1	ISGA	31
11.5.2	Percentage of Total BSA Affected by AD	31
11.6	Tolerability Assessments	31

11.7	Adverse Event Evaluations	32
11.8	Blood Sampling for Chemistry and Hematology.....	32
11.9	PK Blood Sampling	32
11.10	Study Drug Administration.....	32
11.11	Treatment Compliance.....	33
11.12	Protocol Deviations	33
12	ADVERSE EVENTS	34
12.1	Definition of an Adverse Event.....	34
12.1.1	Definition of a Serious Adverse Event.....	34
12.2	Severity of Adverse Events	35
12.3	Relationship of Adverse Events to Study Drug	35
12.4	Documentation of Adverse Events.....	35
12.4.1	Additional Reporting Requirements for Serious Adverse Events.....	36
12.5	Pregnancy	37
12.6	Study Contacts.....	37
13	STUDY TREATMENTS	38
13.1	Description of Study Drug	38
13.2	Area(s) of AD to Be Treated.....	38
13.3	Study Drug Administration.....	38
13.4	Randomization	39
13.5	Masking/Unmasking.....	39
13.6	Study Drug Handling and Dispensing	39
13.6.1	Packaging and Labeling	39
13.6.2	Storage.....	40
13.7	Accountability.....	40
13.8	Return and Destruction	40

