14.2 Sample Size and Definition of Evaluable Subjects

The sample size for this study (approximately 24 subjects in each of Cohorts 1, 2, and 3) is in order to achieve ≥ 20 evaluable subjects (as defined in Section 14.3.2) within each cohort. This sample size is not based on statistical considerations and is instead intended to be a reasonable number of subjects upon which to gather both safety (including the potential to suppress the HPA axis) and systemic exposure information under maximal use conditions of Clobetasol Topical Oil in pediatric subjects. Additional subjects may be enrolled if necessary to achieve ≥ 20 evaluable subjects within each cohort.

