14.4 Statistical Methods

All parameters will be analyzed based on the safety population. Additionally, HPA axis function will be analyzed on the population evaluable for HPA axis function, and PK data will be analyzed on the population evaluable for PK.

In general, categorical and binary variables will be summarized by the frequency count (n) and percentage (%) of subjects with non-missing data per category, and continuous measures will include the number of subjects (N), arithmetic and geometric mean (where appropriate), standard deviation (SD), median, minimum, maximum, and CI (where appropriate).

At the completion of Cohorts 1 and 2, interim results (i.e., cohort-specific data) will be summarized for both the safety and evaluable populations, by visit where appropriate. The parameters and statistics will be reviewed to determine enrollment of the subsequent cohort.

All analyses will follow a prospectively approved statistical analysis plan (SAP). The SAP will be approved before final data lock and before any analyses of the data. The SAP will include the details of all analyses, all database specifications and conventions, and all tables, listings and figures.

Concomitant medications will be coded using the World Health Organization Drug Dictionary (WHO-DD).

All AEs will be recorded and classified using terminology from the Medical Dictionary for Regulatory Activities (MedDRA).

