14.4.7 Interim Analyses and Decision to Proceed to the Next Cohort

No interim analyses are planned for this study. However, safety data will be summarized (as necessary) and reviewed after each cohort, to support a decision as to whether to enroll the next, progressively younger age cohort. The decision to progress to the next cohort will be made by the medical monitor in conjunction with the sponsor.

Safety data that will be reviewed for the most recently completed cohort, before the decision is made to proceed with the next younger cohort, include at a minimum:

- Number and percentage of subjects with HPA axis suppression at the End of Treatment visit, in the safety population. The percentage of subjects with HPA axis suppression at the End of Treatment must be $\leq 40\%$; however, the medical monitor together with the sponsor may use judgment as to whether to exclude from this calculation subjects whose HPA axis suppression may have been due to administration of a prohibited medication (such as other topical corticosteroids) known to affect HPA axis function.

- Number and percentage of subjects with TEAEs in the safety population, and tolerability parameters in the safety population. The medical monitor together with the sponsor may decide not to proceed with enrollment into the next, progressively younger cohort if the frequency, severity, seriousness, and/or nature of TEAEs or tolerability findings are unexpected, taking into consideration the known effects of topical corticosteroids and the potency of CP 0.05%.
- Clinically significant treatment-emergent clinical laboratory (hematology and chemistry) findings in the safety population at the End of Treatment visit. The medical monitor together with the sponsor may decide not to proceed with enrollment into the next, progressively younger cohort if the frequency, severity, seriousness, and/or nature of clinical laboratory findings are unexpected, taking into consideration the known effects of topical corticosteroids.

The medical monitor and sponsor representative will document and communicate their joint decision to the investigator before enrollment of the next, progressively younger cohort is allowed to proceed.

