12.2 Laboratory Evaluations

Clinical laboratory (chemistry and hematology) values at Screening and at the End of Treatment visits will be presented using descriptive statistics. Data from unscheduled visits will be included in the subject listings.

The number and percentage of subjects with HPA axis suppression, defined as a post-stimulation serum cortisol concentration $\leq 18 \mu\text{g}/100 \text{ mL}$, will be presented by visit.

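### The SAP reports HPA axis suppression, from at most 8 subjects, as a count and percentage with no confidence interval

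*Protocol*

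**What the plan says.** **SAP.** Section 4.3 makes safety, including the potential to suppress the HPA axis, the primary objective, and section 4.5 lists HPA suppression first among the three safety endpoints it keeps. Section 12.2 gives the analysis: "The number and percentage of subjects with HPA axis suppression, defined as a post-stimulation serum cortisol concentration" at or below 18 µg/100 mL, by visit. Section 6 limits binary variables to frequency and percentage of non-missing data and names no confidence interval for any type of variable. Table 14.3.6.2 presents the result for the Safety and Evaluable populations. Sections 4.1 and 4.6 record that the study ended during Cohort 1 with 8 subjects enrolled and none in Cohorts 2 or 3.

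**Protocol.** Section 14.4 has the same convention: "categorical and binary variables will be summarized by the frequency count (n) and percentage". Confidence intervals appear there only for continuous measures, where appropriate; section 14.1.2 requires them for Cmax and AUC(0-6). On sample size, section 14.2 says: "This sample size is not based on statistical considerations". The suppression percentage was also a progression criterion. The Synopsis says "Enrollment into Cohorts 2 and 3 will proceed only if the percentage of subjects with HPA axis suppression" in the preceding cohort is at most 40%, and section 14.4.7 repeats it for the safety population: "The percentage of subjects with HPA axis suppression at the End of Treatment must be" at or below that figure.

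**The concern.** A proportion from a handful of subjects says little without its precision. The protocol planned intervals for the exposure parameters but not for the suppression proportion, and the SAP plans none. Because the sample size has no statistical basis, no precision statement elsewhere fills the gap.

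The SAP serves an abbreviated safety report, and Table 14.3.6.2 is its only summary table of HPA suppression. A cell showing 0% or 12.5% without an interval does not tell the reader that a much higher true rate is compatible with the data. Small counts of this kind do get used: protocol section 5.2 cites the absence of suppression in 9 completing adults as part of its case for a favourable profile in children, and in the same section says children are at greater risk than adults.

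**Working it through.** **The plan's own figure.** There is no power or precision calculation to reproduce. The arithmetic is consistent: 3 × 24 = 72. Moving from 24 enrolled to 20 evaluable implies a non-evaluable fraction of 1 − 20/24 = 16.7%, which the protocol does not state.

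**Inputs.**
- Number enrolled: 8 (SAP 4.1, 4.6). This is a ceiling for the number with an End of Treatment test, which the SAP does not give.
- Counts suppressed: none are reported, so every x below is hypothetical.
- Confidence level: neither document gives one. Two-sided 95% is an assumption.

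**Exact (Clopper-Pearson) interval for x of n.**
- Lower limit: 2.5% quantile of Beta(x, n − x + 1), taken as 0 when x = 0.
- Upper limit: 97.5% quantile of Beta(x + 1, n − x). When x = 0 this reduces to 1 − 0.025^(1/n).

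For 0/8 the upper limit is 1 − 0.025^(1/8) = 1 − 0.6306 = 0.369.

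| x/n | Percentage | Exact 95% CI |
|---|---|---|
| 0/8 | 0% | 0 to 36.9% |
| 1/8 | 12.5% | 0.3 to 52.7% |
| 2/8 | 25% | 3.2 to 65.1% |
| 3/8 | 37.5% | 8.5 to 75.5% |
| 0/7 | 0% | 0 to 41.0% |
| 0/6 | 0% | 0 to 45.9% |

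The Wilson method gives lower upper limits (32.4% for 0/8, 47.1% for 1/8, 59.1% for 2/8) but the same picture. The Evaluable population can have no more subjects than the Safety population, so its intervals rest on the same n or fewer.

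**Progression criterion, as a design matter only.** Section 14.4.7 applies it in the safety population, planned at "approximately 24 subjects in each of Cohorts 1, 2, and 3". The largest count meeting it is the integer part of 0.40 × 24 = 9.6, that is 9. If only 20 subjects had data it would be 0.40 × 20 = 8. The chance of meeting it is P(X ≤ 9) for Binomial(24, p), or P(X ≤ 8) for Binomial(20, p).

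| True rate | n = 24 | n = 20 |
|---|---|---|
| 30% | 0.85 | 0.89 |
| 40% | 0.49 | 0.60 |
| 50% | 0.15 | 0.25 |
| 60% | 0.02 | 0.06 |

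The largest qualifying counts have exact 95% intervals of 18.8 to 59.4% (9/24) and 19.1 to 63.9% (8/20).

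**The case against.** The strongest reply is that this is a small descriptive study with no hypothesis test, stopped early and reported in abbreviated form. The SAP gives the number as well as the percentage, shows both populations, and provides a by-subject listing (Listing 16.2.6). With at most 8 subjects a reader can see every result and work out an interval. Neither document claims that risk is absent. All of this is correct, and it means the omission is not an error or a contradiction. It does not remove the case for an interval: a confidence interval is itself descriptive, the protocol already lists it among its descriptive statistics, and naming the method in advance avoids choosing one after the results are seen.

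Three stronger readings are tempting, and the documents do not support them.

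- A reader might infer that younger children were, or are about to be, exposed on the strength of an imprecise percentage. A cohort had to be completed before review, Cohort 1 was not, and no younger cohort was enrolled.
- A reader might infer that meeting the 40% criterion by itself opened the next cohort. It was necessary but not sufficient: adverse events, tolerability and laboratory results also had to "have been reviewed and agreed to be acceptable for progression to the next cohort". The medical monitor and sponsor could decline to proceed on those grounds, and "may use judgment as to whether to exclude from this calculation subjects whose HPA axis suppression" might have been due to a prohibited medication. The probabilities above therefore describe one criterion, not enrolment.
- A reader might infer that the upper confidence limit should be held to 40%. Section 14.4.7 sets the rule on the observed percentage. The two-sided upper limit is at or below 40% only up to 4/24 or 3/20, against 9/24 or 8/20 under the rule as written, so this would be a different and stricter rule.

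**Conclusion.** The point holds for the SAP. An outcome within its primary objective is to be summarised from at most 8 subjects without any measure of precision. Even no suppressed subjects among 8 would leave an exact upper limit of 36.9%, and one would raise it to 52.7%. If only 7 or 6 subjects had an End of Treatment test, a zero count would leave 41.0% or 45.9%.

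These figures assume a two-sided 95% level, the Clopper-Pearson method and illustrative counts; none is a trial result. The change is worth making because it alters what the report can be taken to show, not because the planned summary is wrong. For the progression criterion the point is a design lesson only, relevant if the protocol is reused.

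**What to change.** **In the SAP.** In sections 6 and 12.2 and Table 14.3.6.2, specify x/n, the percentage and an exact (Clopper-Pearson) two-sided 95% confidence interval for the End of Treatment suppression rate, in the Safety and Evaluable populations. Screening needs no interval, because a normal response there is an entry requirement.

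**In the study report.** State the upper limit wherever the suppression rate is described, and note that the cohort-progression criterion was never applied.

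**Cost.** One extra table column and a few sentences. The downside is that the result looks less favourable.

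**Only if the protocol is reused.** Show the same interval descriptively in the section 14.4.7 cohort review, leaving the 40% rule on the observed percentage unchanged. In section 14.2, state the chance of meeting that one necessary criterion at several true rates, for example 0.15 at a true rate of 50% with 24 subjects, or 0.25 if only 20 have data.
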